Study Protocol

Feasibility of Home Monitoring after Primary Total Knee Arthroplasty

Principal Investigator: [name]

Email: [contact]

Background

Over one million primary total hip and total knee arthroplasties (TKAs) are being performed annually in the United States, and it is projected that 1.26 million TKAs will be performed by the year 2030.¹ Simultaneously, there is a projected shortage of trained orthopaedic surgeons to care for these patients.² Telemedicine and innovative home-based technologies to monitor patient outcomes after surgery have gained increasing attention.³ This was possible due to the recent technological advances in telecommunication, allowing the development of commercially-available, easily-accessible, and low-cost home monitoring and virtual rehabilitation systems to allow clinicians to monitor the patient's adherence to post-operative rehabilitation and treatment protocols, particularly for relatively low-risk patients in which a normal recovery is expected.

Recently, emerging evidence has shown that home monitoring systems may have comparable efficacy to conventional follow-up clinic visits in monitoring patient progress postoperatively.⁴⁻⁷ Studies have also shown this technology may aid in lowering the cost of healthcare delivery to these patients while they are being monitored in real-time.^{8,9} In addition, it has been shown that postoperative interventions cost between 37% to 40% of the total episode payment for primary total joint arthroplasty.¹⁰ Therefore, with the recent paradigm shift from "volume-based" to "value-based" healthcare, the use of modern technology allowing optimal patient outcomes while decreasing cost becomes extremely relevant.¹¹

Objectives

In this pilot study, the objective was to assess a novel technology for postoperative home-based monitoring and communication for patients who underwent primary TKA. We specifically evaluated 1) the accuracy of patient mobility and knee range of motion (ROM) measurements obtained using home-based monitoring, and 2) the ability of the technology to monitor physical therapy compliance and collect patient-reported outcomes.

Eligibility

Data will be prospectively collected from a total of 10 patients over the age of 18 years who are scheduled for elective primary TKA. All enrolled patients must meet the following eligibility criteria.

Inclusion Criteria:

1. Scheduled for unilateral primary TKA
2. Reside within 75 miles (driving distance) from the hospital
3. Expected to be discharged home with hospital home care
4. Have wireless internet connectivity in their home

Exclusion Criteria:

1. Scheduled for revision or simultaneous bilateral TKA
2. English is not considered their preferred language for healthcare discussions
3. Body mass index (BMI) greater than 45 kg/m²
4. Enrolled in another research study

Methods

The monitoring technology that will be used in this study was developed by Vivanta Care (Chagrin Falls, Ohio, USA). The system consists of two sensors, each attached to an adjustable strap. One sensor is to be worn 4-6 cm above the knee and the other sensor is to be worn 4-6 cm below the knee and are used together to capture knee ROM. Patients will be instructed to wear these sensors during seated flexion and extension home exercises that are prescribed by the physician (up to 3 times per day) as part of their home therapy routine. Additionally, an activity sensor that tracks the number of steps taken is included for patients to wear on their wrists. Information collected with all three sensors will be transmitted securely between the patient and health providers through an application on a tablet computer that is supplied to each patient preoperatively once he/she consents to participate in the study. This application is also utilized as a timer for the timed up and go (TUG) test, to collect patient reported outcomes, and to guide the patient through the prescribed home therapy exercises. Patients are provided with instructions to connect to the existing wireless internet at home prior to the date of surgery to confirm the connection. Proper installation is verified automatically by the tablet computer cloud server and all communication pathways (sensor ↔ tablet computer ↔ internet ↔ health provider) are verified automatically.

Data Collection:

All patient-reported and functional measurements will be collected electronically via the in-home monitoring system at the intervals specified in the table below and manually by a clinician preoperatively, during one homecare visit per week, and at the 4, 8, and 12 week clinical follow-up visits. The Knee injury and Osteoarthritis Outcome Score (KOOS) consists of 5 subscales (Pain, other Symptoms, Function in daily living, Function in sport and recreation, and knee related Quality of life (QOL)). However, we will only assess KOOS Pain, Function (using the KOOS – Physical Function Shortform) and QOL for this study. Each section is scored independently from the others on a 0-to-100 transformed scale, where zero represents extreme knee problems and 100 represents no knee problems. Functional measures such as the maximum attainable ROM and the number of steps taken will be tracked using sensors worn by the patient. The ROM sensor values will be verified with range of motion measurements taken using a goniometer during therapy and MD visits. Patients will be asked to return all equipment at the time of their 12 week clinic visit.

Outcome Type	Scale	Frequency	
		Electronically Monitored	Collected at Follow-up Visit
Patient-Reported	KOOS Pain	qwk	q4wk
	KOOS Function	qwk	q4wk
	KRQoL	qwk	q4wk
	VAS Pain	tid	q4wk
Function Measure	ROM	tid	q4wk
	TUG	tid	q4wk
	Rehabilitation Compliance	qd	q4wk

qwk = every week; q4wk = every 4 weeks; tid = three times a day; qd = every day; KOOS = Knee injury and Osteoarthritis Outcome Score; KRQoL = knee related quality of life; VAS = visual analog scale; ROM= range of motion; TUG = timed up and go.

Statistical Analysis

A sample of 10 patients will be used as a proof of concept and can be used to refine future sample size calculations. Statistical analysis will be primarily descriptive. The Wilcoxon signed-rank test will be used to evaluate the agreements between the home-monitoring and clinician-based measurements to yield a concordance correlation coefficient that represents a measure of reliability of the method.

References

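### The plan does not say how repeated home-versus-clinician pairs from the same patient are handled, and the signed-rank test it names does not measure agreement or yield a CCC

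*Combined protocol and SAP*

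**What the plan says.** All places are in the combined protocol and SAP.

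- **Clinician readings.** The Data Collection text has all measures recorded by the home system and also "manually by a clinician preoperatively, during one homecare visit per week, and at the 4, 8, and 12 week clinical follow-up visits". The table under that text lists clinician collection only every 4 weeks and does not show the weekly homecare readings. How long homecare lasts is not stated.
- **Home readings.** The table has ROM, TUG and VAS pain collected at home three times a day, the KOOS-based scores weekly and compliance daily.
- **Link between the two.** For ROM: "The ROM sensor values will be verified with range of motion measurements taken using a goniometer during therapy and MD visits". No text says which home reading is compared with which clinician reading.
- **Analysis.** "Statistical analysis will be primarily descriptive", and then: "The Wilcoxon signed-rank test will be used to evaluate the agreements between the home-monitoring and clinician-based measurements to yield a concordance correlation coefficient". The section gives no unit of analysis, no method for repeated pairs, no significance level and no success criterion. Of the sample of 10 it says that it "can be used to refine future sample size calculations".

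**The concern.** There are two problems in the same sentence of the analysis section.

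First, the schedule produces several pairs per patient, while the named test treats every pair as independent. The same knee, sensor set and user supply all of a patient's pairs, so their differences may be correlated. If the pairs were pooled, 10 patients would be analysed as 30 or more independent observations.

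Second, the test does not answer the question. The first objective is the accuracy of the home measurements. A signed-rank test asks whether paired differences are centred on zero. Large errors that balance in sign can leave it non-significant, and a trivial offset in the same direction in every patient can make it significant. The CCC is a separate calculation and does not come out of the test.

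At stake are how the accuracy result is read and how precise it appears when a later study is planned from it.

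**Working it through.** **Inputs from the documents.** There are 10 patients (Eligibility; Statistical Analysis) and clinic visits at weeks 4, 8 and 12 (Data Collection). The figure of 10 comes with no power or precision calculation, so there is nothing to reproduce.

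**Assumptions.** The documents give none of the following:
- correlation of differences within a patient (ICC) of 0.1–0.5;
- nominal two-sided level of 5%;
- 12 pairs per patient as the case where weekly readings run to week 12.

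**Step 1: pairs.** Clinic visits alone give 3 × 10 = 30 scheduled pairs per measure. Weekly readings to week 12 would give 12 × 10 = 120. Missed visits or unusable home data would lower both.

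**Step 2: effect of pooling.** With m pairs per patient, the design effect is DE = 1 + (m − 1) × ICC and the effective number of pairs is 10m/DE. A hand approximation to the rejection rate under no true shift is 2 × [1 − Φ(1.96/√DE)]. For m = 3 and ICC 0.5, DE = 2.0 and 1.96/1.414 = 1.386, which gives 16.6%. The simulated columns use normal differences with mean zero and equal correlation between visits. The last column is the coverage of a nominal 95% t interval for the mean difference from pooled pairs.

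| m | ICC | DE | Effective pairs | Hand approximation | Simulated type I error | Simulated coverage |
|---|---|---|---|---|---|---|
| 3 | 0.1 | 1.2 | 25.0 of 30 | 7.4% | 7% | 93% |
| 3 | 0.3 | 1.6 | 18.8 of 30 | 12.1% | 12% | 88% |
| 3 | 0.5 | 2.0 | 15.0 of 30 | 16.6% | 16% | 83% |
| 12 | 0.1 | 2.1 | 57.1 of 120 | 17.6% | 17% | 82% |
| 12 | 0.3 | 4.3 | 27.9 of 120 | 34.5% | 34% | 65% |
| 12 | 0.5 | 6.5 | 18.5 of 120 | 44.2% | 44% | 55% |

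At ICC 0 both analyses are correct (about 5% and 95%). If the correlation decays between visits (adjacent values 0.1–0.5), the type I error with 3 pairs is 6%–15%.

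**Step 3: valid alternatives.** A signed-rank test on one mean difference per patient, or a separate test at each visit, stays at about 5%. The t interval from patient means covers 95%.

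**Step 4: what the test can show.** With 10 differences all of the same sign, the exact two-sided p-value is 2/2¹⁰ = 0.002, however small the differences are. The p-value therefore says nothing about whether the error is small enough to accept.

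**Step 5: pooled and by-visit CCC are different quantities.** With no mean bias, CCC = 2V/(2V + e²), where e is the SD of the home-minus-clinician differences. V is the between-patient variance, plus the variance of visit means when visits are pooled. As an illustration, take a between-patient SD and e of 8 degrees each (assumed):
- Within a visit: 128/(128 + 64) = 0.67.
- Pooled, visit means with SD 5 degrees: V = 64 + 25 = 89, and 178/(178 + 64) = 0.74.
- Pooled, visit means with SD 10 degrees: V = 64 + 100 = 164, and 328/(328 + 64) = 0.84.

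The device error is the same in all three. A pooled CCC is legitimate, but it has to be labelled as pooled.

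**The case against.** The strongest reply is that the plan never says it will pool. That is right. A reader might infer that the test is invalid as written, but the text fits a by-visit analysis equally well, and each such test would be valid. The inflation also depends on an ICC that the documents do not give. Strap placement, which Methods allows to vary within a 4–6 cm band, could lower it.

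The second reply is that this is a 10-patient descriptive pilot. A reader might infer that a trial conclusion would be wrong. The documents set no significance level or decision rule, so no formal decision can fail. The planning harm is modest too. With 3 pairs the pooled SD of differences is biased by only about 1%–3%. Its effective degrees of freedom are about 28 down to 19 against a nominal 29, so its relative standard error, 1/√(2 × df), goes from 13% to 13%–16%.

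The third reply concerns pairing. The goniometer sentence ties the ROM comparison to therapy and physician visits and can be read as a same-session check. That is a partial anchor. A reader might also take the phrase "Functional measures such as the maximum attainable ROM" to mean the best of three daily readings, and so infer an upward bias in the home values. The documents do not support this, because the phrase can equally mean end of range within one session, which a goniometer would also record.

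What stands is that the plan does not choose among these analyses, does not select among the day's home readings, and attributes a CCC to a test that does not produce one.

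**Conclusion.** The point holds in a limited form and should be corrected before analysis. The plan schedules at least 3 postoperative pairs per patient per measure and leaves their handling open. It rests agreement on a test of shift that assumes independence and yields no CCC. Pooling is one permitted reading, not a stated intention. Under pooling with an assumed ICC of 0.1–0.5, the type I error is about 7%–16% with 3 pairs and 17%–44% with 12, and a nominal 95% interval covers about 93%–83% and 82%–55%. Under by-visit or per-patient use, or at ICC 0, there is no inflation. The mismatch between the test and the accuracy objective does not depend on the ICC. The consequence is a reported accuracy that may be misread and may look more precise than it is.

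**What to change.** Replace the agreement sentence in Statistical Analysis with:

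> The patient is the unit of analysis. For ROM, TUG and the patient-reported scores we report the mean home-minus-clinician difference with a t-based 95% interval from one mean difference per patient with at least one pair, and Bland-Altman limits of agreement for repeated observations per patient. The CCC is computed separately from any test and reported by visit (weeks 4, 8, 12); any pooled CCC is labelled as such. Any signed-rank test uses one mean difference per patient.

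The sponsor should also state, before data are seen, which home reading is paired with each clinician reading. The Data Collection text and its table must be reconciled on the weekly homecare readings, since that settles how many pairs exist. Rehabilitation compliance is left out of the wording because a daily home record may not correspond to what the clinician records every 4 weeks.

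**Cost.** The change needs wording and minor programming, with no extra patients, visits or data. At ICC 0.1–0.5 the interval for the mean difference is wider than a pooled one by a factor of about:
- 1.2–1.6 with 3 pairs;
- 1.4–2.1 with 6 pairs;
- 1.6–2.9 with 12 pairs.

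At ICC 0 the factor is about 1.1. A by-visit CCC from 10 patients is imprecise: at an assumed true value of 0.67, 95% of estimates fall between about 0.10 and 0.89. It can also average slightly below a pooled CCC even when visit means are equal (about 0.60 against 0.61–0.64 in simulation).

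### The agreement analysis cannot be run as written: a Wilcoxon signed-rank test neither measures agreement nor produces a concordance correlation coefficient, and repeated pairs per patient are not addressed

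*Combined protocol and SAP*

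**What the plan says.** The Objectives section sets out, as the first of two aims, to evaluate "the accuracy of patient mobility and knee range of motion (ROM) measurements obtained using home-based monitoring". Under Data Collection the reference standard for range of motion (ROM) is given: "The ROM sensor values will be verified with range of motion measurements taken using a goniometer during therapy and MD visits". Clinician measurements are taken "manually by a clinician preoperatively, during one homecare visit per week, and at the 4, 8, and 12 week clinical follow-up visits", which is at least four occasions per patient before any homecare visits are counted. The table in that section has home ROM recorded "tid" and clinician ROM every four weeks.

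The Statistical Analysis section is short. It states "Statistical analysis will be primarily descriptive" and then names one method: "The Wilcoxon signed-rank test will be used to evaluate the agreements between the home-monitoring and clinician-based measurements". The same sentence goes on to give the purpose of that test, which is said to be "to yield a concordance correlation coefficient that represents a measure of reliability of the method". No other method for accuracy or agreement is named. There is no alpha, acceptance threshold, rule for pairing readings, analysis time point or treatment of within-patient correlation. On sample size it says "A sample of 10 patients will be used as a proof of concept and can be used to refine future sample size calculations".

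**The concern.** The sentence makes the CCC an output of the signed-rank test. The test uses only the signs and ranks of the paired differences and asks whether they are centred on zero. It says nothing about how far apart the two methods are for an individual patient, which is what accuracy and agreement mean here. An analyst following the sentence literally has a p-value and no route to the coefficient.

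The stake is objective 1. If the p-value were read as the verdict, a very noisy sensor with no average bias would usually pass, and a very precise sensor with a trivial constant offset could fail. The stated use of the sample for later sample size planning also suffers, because planning an agreement study needs the bias and the SD of the differences, and a signed-rank p-value gives neither.

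A second gap follows from the schedule. Each patient supplies several clinician readings. If all pairs were treated as independent, the test, and any interval added to it, would claim more information than 10 patients hold.

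**Working it through.** The plan gives no figure to reproduce: the 10 patients are stated without a calculation. The check is therefore of the method.

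**1. Can a CCC be derived from a signed-rank result?** Take ten constructed pairs: reference values x = 80, 85, …, 125 degrees, and differences d = k × (1, −2, 3, −4, 5, −6, 7, −8, 9, −10). The positive ranks sum to 1 + 3 + 5 + 7 + 9 = 25 and the negative ranks to 30, so W = 25 and the exact two-sided p = 0.846 for every k > 0.

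The CCC is 2·cov(x, y) / [var(x) + var(y) + (mean difference)²]. The limits of agreement are the mean difference ± 1.96 × SD of the differences, and that SD is 6.519k. With var(x) = 206.25 (divisor n):

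| k | W, p | CCC | Half-width of limits (degrees) |
|---|---|---|---|
| 0.1 | 25, 0.85 | 409.75 / 410.135 = 0.999 | 1.3 |
| 1 | 25, 0.85 | 385 / 423.5 = 0.909 | 12.8 |
| 2 | 25, 0.85 | 357.5 / 511.5 = 0.699 | 25.6 |
| 3 | 25, 0.85 | 330 / 676.5 = 0.488 | 38.3 |

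One test result is compatible with near-perfect and with poor agreement. This step needs no assumed alpha or variance.

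The two can also point in opposite directions. With ten other constructed pairs, a sensor reading about 1 degree high for everyone gives p = 0.002 (the smallest possible two-sided value at n = 10, 2/2¹⁰) with CCC 0.998. Errors of 15 to 31 degrees balanced in sign give p = 1.00 with CCC 0.39.

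**2. What if the p-value were used as the verdict?** The documents give no variances, so these are assumptions: true ROM SD 12 degrees, normal differences, two-sided 0.05, one independent pair per patient. The population CCC is 2·144 / (2·144 + SD² + bias²). Simulated chance of a non-significant result:

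- No bias, error SD 20; CCC = 288/688 = 0.42: about 95% at 10, 30 or 100 pairs. More data never exposes the noise.
- Bias 5, error SD 10; CCC = 288/413 = 0.70: 72% at 10 pairs, 27% at 30, 0.2% at 100.
- Bias 1 at 10 pairs: about 0% with error SD 0.5 (CCC 0.996), 22% with SD 1, 72% with SD 2 and 85% with SD 3 (CCC 0.966). The more precise the sensor, the more often it would fail.

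**3. Repeated pairs.** Take the three clinic visits for 10 patients, pooled as 30 pairs, with no average bias. The effective number of pairs is 30 / [1 + (3 − 1) × ICC], where ICC is the assumed within-patient correlation of the differences: 30/1.6 = 18.8 at 0.3 and 30/2.0 = 15 at 0.5. Simulated results:

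| Assumed ICC | False-positive rate, pooled test | Coverage of nominal 95% CI for bias, pooled |
|---|---|---|
| 0 | about 5% | about 95% |
| 0.1 | about 7% | about 93% |
| 0.3 | 12% | 88% |
| 0.5 | 17% | 83% |

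At ICC 0.3 and 0.5, using one mean difference per patient brings these back to about 5% and 95%. With four pairs per patient the pooled false-positive rates at 0.3 and 0.5 are 16% and 20%.

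**The case against.** The best defence is that the authors meant two things: a CCC as the measure of reliability and a signed-rank test as a check for systematic difference. The CCC is a sound agreement statistic and is named in the plan, so the fault may be one bad connecting phrase. The study is also a 10-patient descriptive pilot with no hypothesis, alpha or go/no-go rule, so no confirmatory error rate is at risk.

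Much of this is fair. It limits the consequences in step 2, which arise only if the p-value is taken as the verdict, a use the plan does not state. It also means that step 3 describes an omission and not an error: nothing says pairs will be pooled, an analysis by visit with one pair per patient would fit the text, and the inflation is small at low correlation. The plan includes no confidence intervals that could be wrong.

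The defence does not rescue the sentence. Even on the generous reading, the plan does not say how the CCC is computed, what the test is for, or which readings form a pair, and no other section supplies this. A descriptive study depends on naming the right descriptive quantity.

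**Conclusion.** The concern holds. As worded, the only analysis named for objective 1 cannot be carried out, and it needs correcting before analysis. That conclusion rests on the wording and on step 1 alone, where an identical test result accompanies CCCs from 0.999 to 0.49.

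The misreading rates in step 2 are conditional on the p-value being used as the verdict and on assumed SDs and biases. The 12% to 17% false-positive rate is conditional on pooling and on an assumed correlation of 0.3 to 0.5. The repeated-pairs point should be read as a gap in the plan. What is affected is whether objective 1 can be interpreted; the data collection itself is not at fault.

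**What to change.** Replace the sentence with wording along these lines:

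> For each measure collected both by home monitoring and by a clinician, agreement will be estimated by the mean difference (bias) with Bland-Altman 95% limits of agreement, and by the CCC computed directly from the paired values, each with a 95% CI. Repeated pairs from the same patient will be handled with repeated-measures versions of these estimates or a bootstrap that resamples patients. The CI for bias will use one mean difference per patient. The signed-rank test, if kept, will be applied to one summary difference per patient as a secondary check for systematic bias. A non-significant result will not be taken as evidence of agreement.

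Two additions are needed to make this executable. First, state which home reading is paired with each clinician reading, since home ROM is recorded up to three times a day, and which visits count: the text includes preoperative and weekly homecare measurements, while the table's visit column shows only four-weekly collection. Second, list the measures to which the analysis applies. Rehabilitation compliance has no defined scale, so limits of agreement may not suit it.

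Separating the CCC from the test is the minimum repair. The limits of agreement are added because they express error in degrees and supply the SD that later sample size work needs.

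The cost is a few sentences, with no new patients, visits or data. The drawback is visible imprecision:

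- With 10 independent pairs, each limit of agreement has a 95% CI of about ± t₉ × √(1/10 + 1.96²/18) = 2.262 × 0.560 = 1.27 SDs of the differences. If that SD were 5 degrees (an assumption), this is about ±6.3 degrees.
- With true ROM SD 12 and error SD 5 (both assumed), the true CCC is 288/313 = 0.92, and sample values at 10 pairs fall mostly between 0.70 and 0.98.
- A percentile bootstrap over 10 patients with three pairs each covered about 87% in simulation instead of 95%, so the CCC intervals should be described as approximate.

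### The planned signed-rank test and single concordance coefficient cannot separate a constant sensor offset from an angle-dependent error, so understated ROM recovery could go unrecognised

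*Combined protocol and SAP*

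**What the plan says.** The Objectives section puts first "the accuracy of patient mobility and knee range of motion (ROM) measurements obtained using home-based monitoring". Under Data Collection, "Functional measures such as the maximum attainable ROM and the number of steps taken will be tracked using sensors worn by the patient", and the reference method is a goniometer: "The ROM sensor values will be verified with range of motion measurements taken using a goniometer during therapy and MD visits". Clinician measurements are taken "manually by a clinician preoperatively, during one homecare visit per week, and at the 4, 8, and 12 week clinical follow-up visits". The table in the same section lists visit ROM only every 4 weeks, and the text does not say how many weeks the homecare visits continue. The number of sensor-goniometer pairs per patient is therefore uncertain.

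The Statistical Analysis section gives one sentence on agreement: "The Wilcoxon signed-rank test will be used to evaluate the agreements between the home-monitoring and clinician-based measurements to yield a concordance correlation coefficient". The coefficient is one "that represents a measure of reliability of the method". The rest is general: "Statistical analysis will be primarily descriptive" and "A sample of 10 patients will be used as a proof of concept and can be used to refine future sample size calculations". The section specifies no plot of differences, limits of agreement, calibration slope, split of the coefficient into its components, comparison of change, or acceptance criterion.

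**The concern.** A sensor can be wrong in two ways that matter differently here. A constant offset shifts every reading and drops out of a change over time. A scale error (say, over-reading a stiff knee and under-reading a flexible one) shrinks every recorded gain. The device is meant to follow recovery, so the second kind does the damage.

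The signed-rank test addresses only the centre of the paired differences, and positive and negative differences can cancel. The concordance coefficient does penalise a scale error, but mildly, and it reports one number for offset, scale error and noise together. At stake is whether a reader of the pilot, or the designer of the next study, takes a favourable coefficient and a non-significant test as evidence that the sensor tracks recovery.

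**Working it through.** **Inputs.** From the protocol: 10 patients, a goniometer as reference, and the visit schedule. The protocol gives no ROM mean, SD, measurement error, alpha or coefficient target, so it has no figure to reproduce. Assumed: between-patient SD 10 degrees; error SD 4 degrees per method; 12 weekly visits with mean ROM rising evenly from 75 to 118, or three visits at 95, 110 and 118; two-sided 0.05; signed-rank test on patient means.

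**Step 1: the coefficient without noise.** CCC = 2·cov / (var_S + var_G + (mean difference)²).
- Slope b turning about the mean gives 2b/(1+b²). For b = 0.90, 1.80/1.81 = 0.994; for 0.85, 1.70/1.7225 = 0.987; for 0.80, 1.60/1.64 = 0.976.
- A constant offset d with SD S gives 2S²/(2S²+d²). With S = 15, the value 0.976 arises at d = √(450 × 0.025) = 3.4 degrees.

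A sensor that loses 20% of every gain and one that is simply 3.4 degrees off therefore get the same coefficient.

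**Step 2: with noise and recovery, weekly pairs.** Variance of the weekly means is (43/11)² × 143/12 = 182.1. Adding 100 between patients gives 282.1. Error variance is 16 per method, so the goniometer variance is 298.1. At slope 0.85, cov = 239.8 and the sensor variance is 0.7225 × 282.1 + 16 = 219.8.

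| Sensor | CCC, closed form | CCC, simulated | Signed-rank rejection | Recorded gain (true 43) |
|---|---|---|---|---|
| No scale error | 282.1/298.1 = 0.946 | 0.94 | 5% | 43 |
| Slope 0.85, zero error mid-range | 479.6/517.9 = 0.926 | 0.92 | about 5% | 36.55 |
| Constant offset −4 | 564.2/612.2 = 0.922 | 0.92 | 100% | 43 |
| Slope 0.85 from 0 degrees | 479.6/(517.9 + 14.475²) = 0.659 | 0.65 | 100% | 36.55 |

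Row 2 understates recovery by 0.15 × 43 = 6.45 degrees and looks acceptable. Row 3 records recovery in full and looks worse. With the three visits only, the row 2 sensor has a coefficient of 0.90 (0.92 with no scale error) and rejection stays near 5%.

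**Step 3: dependence on where the error crosses zero.** At slope 0.85 with weekly pairs, moving the crossing point 10 degrees below the mean creates a mean bias of 0.15 × 10 = 1.5 degrees, and rejection rises to 45–49%. At 20 degrees below it is 96%, and at 30 degrees 100%. If all pairs were pooled as independent, a mid-range slope of 0.80 would be rejected 8–22% of the time (4 or 12 visits, error SD 2 to 4), against 4–7% for a perfect sensor.

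**Step 4: what would separate the errors.**
- *Paired difference in change.* For each patient, take the sensor change minus the goniometer change. An offset cancels, and the expected value is (b − 1) × true change. Its error SD is √(4 × 16) = 8, so with 10 patients the SE is 8/√10 = 2.53 and the 95% half-width is 2.262 × 2.53 = 5.7 degrees. The expected value is −6.45 for the weekly series (detected about 62% of the time) and −0.15 × 23 = −3.45 for weeks 4 to 12 (about 25%). With unequal error SDs of 8 (sensor) and 3 (goniometer), it stays unbiased with about 5% false rejection; the half-width grows to 2.262 × √(128 + 18)/√10 = 8.6.
- *Within-patient trend of the difference.* Over 12 weekly pairs, the SD of the fitted change is 11 × √(32/143) = 5.2 instead of 8. With three equally spaced visits it equals the first-to-last comparison.
- *Regression of difference on mean.* The slope is [(var_S − var_G)/2] / [(var_S + var_G + 2cov)/4]. At slope 0.85 with equal errors it is −39.15/249.4 = −0.157, detected about 98% of the time weekly and 38% with three visits. With error SDs 8 and 3 and no scale error it is 27.5/300.4 = +0.09, falsely significant about 45% of the time weekly. With those SDs and a true 0.85 it is −11.65/259.6 = −0.045, detected about 10% of the time. This regression can invent or hide a scale error.

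**The case against.** The strongest reply is that the favourable picture needs the error to cross zero near the middle of the observed range, and nothing in the protocol suggests it does. Step 3 bears this out: away from mid-range the signed-rank test increasingly rejects, and an error proportional from 0 degrees is always flagged. A reader might infer that any sensor which under-reads gains would look accurate. That does not follow. Where the discrepancy is flagged, what remains is narrower: the planned statistics show that the methods differ, not that the difference grows with angle.

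A reader might also infer that the plan would declare Objective 1 met. The plan has no threshold and calls its analysis descriptive, so nothing is formally passed or failed. Nor do the documents give evidence that this sensor has a scale error.

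It can also be said that the components are computable later from the same pairs. That is true: no data are lost, and the gap is in what is prespecified. Finally, the quoted sentence has a plainer fault, since a signed-rank test does not produce a concordance coefficient. Correcting that would leave this gap in place.

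**Conclusion.** The point holds in a limited form. Neither planned statistic separates an offset from an angle-dependent error. If the error crosses zero near mid-range, both can look favourable while recovery is understated by 15% at slope 0.85. If it is proportional from 0 degrees, the discrepancy is seen but its nature is not. The algebra in Step 1 needs no trial data; the other sizes rest on the assumed ROM means, SDs, error SDs, slopes and crossing points. The consequence is a possible misreading of sensor accuracy in a 10-patient proof of concept, not an invalid confirmatory conclusion. The change is worth making because it is cheap and the pilot is meant to inform later work.

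**What to change.** Add two items to the Statistical Analysis section, using the ROM pairs already planned.

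1. For each patient, compute the change in ROM from the first to the last postoperative paired visit by sensor and by goniometer, or the within-patient trend of sensor minus goniometer over all postoperative pairs. Report the mean paired difference with a 95% CI beside the mean bias. Specify postoperative pairs, because clinician measurement starts before surgery and a preoperative-to-final change is not recovery.
2. Show a difference-versus-mean plot as a descriptive display only. If a slope is quoted, give a patient-clustered CI and state that it assumes equal error variance in the two methods.

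I would not extend this to TUG, for which the documents give no mechanism for a scale error. Nor would I restrict accuracy statements to an angle range where the bias looks small: that range would be chosen from 10 patients' data without a definition of small.

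The cost is a few sentences and a short analysis, with no new measurements. The downside is wide intervals, especially if only the week 4, 8 and 12 pairs exist. Report estimates with intervals, not a test.
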